6.2 Materials Transfer Information

Stored samples and/or data may be sent to outside collaborating laboratories, or shared with other NIH collaborating investigators, to study questions related to diabetes or its complications (including, for example: microbiome sequencing, stool metabolite analysis, diabetes, obesity, weight, and lipid metabolism). Samples may be sent to outside commercial laboratories for analysis. Samples and data sent to outside laboratories and collaborators for analysis and/or testing will contain only coded numbers, without personal identifiers. Materials Transfer Agreements will be completed before the exchange of samples and/or data with outside collaborators.

6.3 Genomic Data Sharing Plan

This protocol involves the collection of non-human genomic DNA. Fecal samples will be stored for analysis of microbial DNA. The participants will consent for their data to be shared through publicly accessible databases over the internet, NCBI or NIH's genebank. Data will be submitted at the time of publication and will include the relevant genomic data and corresponding phenotypic data. Users must agree to the conditions of use governing access to the public release data, including limitation of research to investigations consistent with the participants' consent, restrictions against attempting to identify study participants, destruction of the data after analyses are completed, reporting responsibilities, restrictions on redistribution of the data to third parties and proper acknowledgment of the data resource.

7.0 Multiple-site Studies

The primary site for study visits will be at the NIH Clinical Center. Primary enrollment and informed consent and assent will only occur at the NIH Clinical Center.

8.2 Informed Consent/Assent Procedures

Informed consent/ assent will be obtained as consistent with the requirements of SOP 12 and 14D. Written consent/assent will be obtained from each subject after detailed explanations of the planned procedures by the principal or a designated

associate investigator. Prospective subjects will be given the research information in layman's term and in language understandable to the subjects. The consent process will take place prior to any study procedures. Subjects have the right to withdraw participation from this protocol at any time.

8.2.1 Language for Minors

Written informed consent and assent will be obtained from the minor and his/her parent/guardian or (LAR) prior to any screening visits, study procedures or interventions. The Principal Investigator or other designated qualified protocol investigators will explain the study in language understandable to the parent/guardian or (LAR)). The investigator will also explain the study to the minor who is of a younger age and level of understanding. Enough time and opportunity will be given for discussion of the research as well as to answer any questions they may have, taking care to minimize or eliminate the perception of coercion or undue influence. In accordance with 45 CFR 46.408, [the parent/guardian or (LAR)], will sign the current IRB approved informed consent. The minor ages 10-17yrs will provide written assent, as we expect that all of those enrolled will be capable of understanding and signing the assent document. The investigator will sign the assent as well. A copy of the consent and assent will be given to the minor and [his/her [parent/guardian or (LAR)] for future reference. The signed documents will be sent to the Medical Records Department for placement in the subject's permanent CC medical record. The consent process will additionally be documented in the electronic medical record (CRIS).

For minors who reach the age of consent while enrolled in our protocol, the parent and the minor will be forewarned at the time of enrollment, that there will be a need to consent the minor on reaching the age of consent as consistent with the requirements of SOP-12 and 14D—Requirements for Informed Consent. This is because the prior parental permission and child assent are not equivalent to legally effective informed consent for the now-adult subject (consistent with NIH HRPP SOP 14D.8). All individuals will be given the opportunity to ask questions. In these situations, reconsenting will be performed at the NIH CC or using the telephone consent process.

8.2.2 Telephone consenting

When executing the consent process by telephone, the subject will receive a copy of the protocol consent in the mail prior to being consented. After they have had an opportunity to review the consent the investigator will contact the subject by telephone. The investigator will review the investigational nature of the protocol with the subject and answer questions. If the subject chooses to participate, the subject will sign and date the consent. The informed consent document will be mailed to the principal or associate investigator who led the discussion, who will sign and date and mail back a fully executed copy for the subject's records. The informed consent process will be documented on a progress note and a copy of the note and the original informed consent will be filed in the subject's record.

8.3 Rationale for Subject Selection

Type 2 diabetes in youth is a rapidly progressive and aggressive disease yet metformin therapy, the only oral- approved anti-diabetic therapy, is associated with GI sides effects in up to 80% of newly initiated patients and up to 30% of patients on chronic therapy. The burden of metformin-related GI side effects is magnified in youth because it is a potentially modifiable reason for medication non-adherence and subsequent poor glycemic control. Therefore, investigating a non-pharmacological supplement that may improve metformin tolerance in youth and young adults is of high clinical significance. Volunteers eligible for this study include mature adolescents and young adults with type 2 diabetes. Young adults will be included in the protocol to enhance recruitment and because the disease progression is similar to adolescents with type 2 diabetes. We will not recruit pre-pubertal or peri-pubertal children with diabetes because this increases the risk that they have type 1 diabetes (a condition not relevant to the aims of the current study).

8.3.1 Rationale for Exclusion of Vulnerable Populations

This study will involve recruitment of children age 10-17 years as described above. The study will not involve recruitment of other vulnerable populations including pregnant women, prisoners, adults who are or maybe unable to give consent because they do not meet the inclusion criteria for this study. We will protect participants as described in SOP 14A.

8.4 Recruitment Strategies

Tools used for the recruitment of subjects will include the posting of the study description on the NIH CC website, the NIH Record, the Clinical Center News, Children's National Medical Center (CNMC), newspaper advertisements and social media). Additionally, fliers will be placed on bulletin boards at different buildings throughout the NIH campus, the CNMC, George Washington University, the University of Maryland and other pediatrician or doctors' office sites in the Washington DC Metropolitan area. Recruitment material will be IRB approved prior to dissemination. Also, potential participants may be referred by local providers responsible for clinical care. This includes the Children's National Multidisciplinary Type-2 Diabetes clinic, as well as from other community providers to whom we will provide our study information and fliers.

8.4.1 Strategies to address the challenges of clinical trials in youth with type 2 diabetes

The research team is experienced in successfully recruiting youth with type 2 diabetes and familiar with the major challenges to pediatric research in type 2 diabetes in youth and young adults: (1) difficulty with recruiting eligible participants and (2) poor retention rates[58]. To maximize recruitment multiple techniques will be employed including: partnering with major organizations in the Washington DC metro area including CNMC, INOVA, Georgetown University, University of Maryland, Kaiser, and Johns Hopkins University, who we will meet with on a periodic basis and provide handouts for them to give to any of their patients who may be interested.

To improve retention in this study we will employ the following strategies including: periodic telephone, e-mail and/ or text message communication, as well as strategizing with individual families regarding their unique socio-economic barriers and offer alternative and supportive strategies to encourage study adherence (e.g. finding creative solutions to transportation issues).

8.5 Risks/Benefits Analysis including Considerations of Alternatives to Participation

This study involves research that is greater than minimal risk but presenting the prospect of direct benefit to the individual subjects.

8.5.1 Evaluation of Benefits

This research protocol is designed to elucidate mechanisms of the side effects caused by metformin and the ability of a supplemental product to improve those in patients who are already requiring metformin. Metformin is approved for the treatment of youth with type 2 diabetes 10 years or older and is standard of care. Limited data (Burton et al 2015) demonstrates that there may be both an improvement in GI symptoms as well as in glycemia for patients with type 2 diabetes, so there is a theoretical possibility that the MM will reduce GI side effects of metformin, and therefore quality of life, and improve blood sugars. Participating in the protocol procedures may also be beneficial to the individual because it may provide specific information about the individual's glycemic control and diabetes management, as well as more frequent interaction with the study team.

8.5.2 Evaluation of Risks

This research protocol will be associated with greater than minimal risk. The specific risks and our approach to minimize these risks are outlined below.

- Blood Sampling: Peripheral blood draws (venipuncture) performed during this study for research will not exceed 10.5 mL/kg, or 550 mL (whichever is smaller) per 8-week period for adults. For pediatric patients, blood draws will not exceed 5 mL/kg in a single day, or 9.5 mL/kg or 550 mL (whichever is smaller) per 8-week period. The total blood volume for this study is 372 ml over the 9-week period. Patients may experience some discomfort at the site of the needle entry, and there is a risk of bruising at the site. There is a remote risk of fainting or local infection.
- 2. Intravenous Catheter Placement: The placement of intravenous catheters can be uncomfortable and pose the potential risk of bleeding, bruising and infection. All catheters will be placed under sterile conditions and universal precautions will be observed. Should any complications occur, they will be addressed immediately.

3. Risk associated with metformin

- i. Gastrointestinal upset: Nausea, vomiting, diarrhea, flatulence, abdominal discomfort and indigestion are common side effects associated with metformin use. To be eligible for this study, participants will have an indication to start metformin as first line therapy for type 2 diabetes, if they are not already taking it prior to the start of the study. The following actions will be taken to minimize the risk for gastrointestinal disturbance:
 - a. Metformin dosing will be dose escalated over a 1-3-day time period
 - b. Gastrointestinal symptoms will be recorded daily by participants and communicated with the study team with each submission of the online questionnaire.
 - c. Participants who experience severe and/or recurrent gastrointestinal symptoms, defined as ≥ 3 diarrheal episodes or intense discomfort or cramping > 3 hours, will be withdrawn from the study.
- ii. Boxed Warning Lactic acidosis (rare): The risk of lactic acidosis with metformin use is increased in elderly individuals with renal dysfunction or congenital heart failure. Participants with chronic renal or heart failure, or other chronic metabolic illnesses will not be recruited for this study.
- iii. Kidney problems: In individuals with kidney failure, diarrhea, nausea and vomiting may cause a loss of fluids and dehydration. Subjects with impaired renal function at baseline evaluation will not be recruited for this study.

4. Risk associated with drug-free periods

i. Severe Hyperglycemia with metabolic decompensation: During the 7-10-day period between Visit 1 and Visit 2, and again in the 21-day period between Visit 3 and 4, youth may be at increased risk for severe hyperglycemia since the youth will be asked to stop their anti-diabetic medication. This risk is reduced because we will only enroll individuals who are in relatively good glycemic control (HbA1c <8%) who will be at lower risk for decompensation. Subjects will receive counseling on diet and lifestyle treatment to minimize this risk, as this is in keeping with current standard of care clinical guidelines as an important treatment modality for youth with type 2 diabetes [59].

The following steps will be taken to minimize the risks of severe hyperglycemia:

- a. Participants at higher risk for severe hyperglycemia defined as those with HbA1c \geq 8% will not be eligible to participate.
- b.All participants will receive up-to-date education on diet and lifestyle management by the PI and study staff.
- c. During the run-in drug free period all individuals will monitor glucose levels by CGM. Those who are unwilling to wear CGM will be required to check 2 fingerstick glucoses per day. Study staff will be in daily contact with participants to review trend uploads.

- d.If CGM or glucometer readings show >200mg/dl fasting, or 300mg/dl bedtime is noted during the run-in period, they will notify the study PI immediately. Individuals with persistently elevated glucose levels and signs and symptoms of metabolic decompensation (e.g. vomiting, dehydration, lethargy, abdominal pain) will be withdrawn from the study and restarted on his/ her medication.
- e. If vomiting, abdominal pain or dehydration is noted, participant will be evaluated by a medical professional or PI immediately for metabolic evaluation of acidosis and ketosis. If metabolic decompensation (acidosis or ketosis) is noted, participants will be promptly treated and withdrawn from the study.
- 5. Stool sampling: Stool sampling is not associated with any health risk but may be uncomfortable for some participants.
- 6. Radiation Exposure: Dual energy absorptiometry (DXA) scan. The DXA scan is a reliable and reproducible method to measure body composition, specifically body fat and lean body mass. The patient lies on a flat table with the x-ray source below the table and the detector above. Each scan takes about 5-7minutes. For the DXA scan the effective dose of radiation is 0.00006 rem, which is below the guideline of 5 rem (or 0.5 rem in children) per year allowed for research subjects by the NIH Radiation Safety Committee. The average person in the United States receives a radiation exposure of 0.3 rem per year from natural sources, such as the sun, outer space, and the earth's air and soil. If participants want to learn more about radiation, they will be given the pamphlet: An Introduction to Radiation for NIH Research Subjects.
- 7. Activity and Sleep monitoring: There are no risk associated with these monitors, but participants may find them inconvenient to wear.
- 8. Continuous glucose monitoring system: According to the device manufacturer, there is minimal risk associated with the device. Possible side effects include but are not limited to local infection, inflammation, pain or discomfort, bleeding at the insertion site, bruising, itching. Because this protocol represents the first use of this device by our research team, we do not know the frequency of such complications of the device. A medical provider will be available should any of these problems occur.
- 9. Risk associated with prebiotic MM: The MM Biome Bliss is a fiber supplement that is available and marketed in the USA. In the dose prescribed for this study, the beta-glucan supplement will be equivalent to ~3cups of cooked oatmeal per day and provide ~ 40% of recommended daily fiber intake. This supplement can uncommonly be associated with minor gastrointestinal upset (stomach bloating, loose stools) and has not been associated with any serious adverse effects.

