Participants will receive instructions on stool collection at home and stool collection kits - one to be mailed back to the study team for analysis prior to stopping their baseline metformin dose (unless they are able to provide a stool sample after consent while still at NIH), and one to collect a sample in the 24 hours prior to visit 2 if has a bowel movement. Patients will also be taught how to fill out daily surveys to assess GI symptoms (see details below). They will meet with a member of the nutrition team to select foods for their metabolic diet and to be educated on completing a 3-day food record. Participants will also be educated on foods we will ask them to avoid during the study, such as pre/pro-biotics (kombucha, kefir, yogurt, etc.) and foods containing non-nutritive sweeteners.

Period 1 (Drug-free run-in, Visit 2 and 3)

Drug-free run-in period: Participants will discontinue metformin for the 7-10 days preceding Visit 2, to assess their metabolic and gut microbiome response off anti-diabetic medications, as well as to wash out the immediate effect of metformin on the participants microbiota. The timing of this 1 week period was chosen because changes in gut microbiome have been observed in as little as 1 day and on average 1 week [33]. During this time, participants will complete daily GI symptom questionnaires and monitor their blood glucose and upload their readings daily while not taking metformin. Participants with persistently elevated fasting glucose readings and/or signs and symptoms of metabolic decompensation (e.g. vomiting, dehydration, lethargy, abdominal pain, ketonuria and acidosis) will be withdrawn from the study and restarted on his/her medication. During the drug-free run-in period, individuals who cannot either wear the continuous glucose monitor (CGM), or complete at least 2 finger stick blood glucose measurements daily will be withdrawn from the study.

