- **Blood glucose monitoring**: Blood glucose will be monitored with either fingerstick blood glucose twice daily (fasting and bedtime) or by using an FDA- approved continuous glucose monitoring device (CGM) (for example, the Freestyle Libre). The device will be used to monitor glucose in real-time, approximately every 5 minutes. The system consists of a small sensor, transmitter, and hand-held receiver. The small sensor, with a small needle attached, will be inserted subcutaneously. The transmitter, which is attached to the sensor, will send the measured glucose to the receiver. The sensor is changed at least once every two weeks. Participants will receive training on removing and replacing the sensor and education on the signs and symptoms of hyperglycemia (see Appendix B). Participants will be asked to upload their readings daily to be monitored by a member of the study team daily while participants are not taking metformin, and weekly while taking metformin. Participants will be asked to contact the study team immediately after confirming with a finger stick BG if their glucose is low (<50mg/dL), or if they have a fasting blood glucose reading of >200mg/dl, or a reading anytime of >300mg/dl. Participants with persistently elevated fasting glucose readings and/or signs and symptoms of metabolic decompensation (e.g. vomiting, dehydration, lethargy, abdominal pain, ketonuria and acidosis) will be withdrawn from the study and restarted on his/her medication.

- Activity and Sleep Monitoring: Free-living physical activity and sleep quality will be quantified using a small, non-invasive, portable watch accelerometer (GT3X+ by Actigraph Inc., Pensacola FL) worn on the participant's wrist. Physical activity levels, sleep duration and efficiency, amount of time spent in sedentary, moderate, vigorous intensity categories and estimated activity-associated energy expenditures will be extracted using established predictive equations. This is an FDA 510(k) cleared Class II medical device.
- Urine sample collection: urine will be collected at every visit for storage; for females, this same sample will be used for a pregnancy test
- **Stool sample collection:** Participants will bring stool samples from home collected in the previous 24 hours to be processed by the study team or stool samples will be collected during outpatient visits. The stool sample will be stored at 4C in a sterile plastic vial and processed same day (see Appendix C).

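### Section 8.5.2 item 4.i.d states a weaker withdrawal rule for the drug-free periods than Sections 3.2 and 3.2.1

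*Combined protocol and SAP*

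**What the plan says.** The protocol states the rule for ending a drug-free period because of hyperglycaemia in three places.

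- Section 3.2, in the paragraph on the drug-free run-in, applies withdrawal and restart of medication to "Participants with persistently elevated fasting glucose readings and/or signs and symptoms of metabolic decompensation".
- Section 3.2.1, under blood glucose monitoring, repeats that sentence without tying it to one period. It has glucose uploads "to be monitored by a member of the study team daily while participants are not taking metformin". It also asks participants to contact the team at once for a fasting value above 200 mg/dL "or a reading anytime of >300mg/dl".
- Section 8.5.2, item 4.i.d, applies withdrawal and restart to "Individuals with persistently elevated glucose levels and signs and symptoms of metabolic decompensation". Its notification sentence begins "If CGM or glucometer readings show >200mg/dl fasting, or 300mg/dl bedtime is noted during the run-in period" and continues "they will notify the study PI immediately".

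Item 4.i.e of 8.5.2 adds a route that starts from symptoms. Dehydration, vomiting or abdominal pain leads to immediate medical evaluation, and then: "If metabolic decompensation (acidosis or ketosis) is noted, participants will be promptly treated and withdrawn from the study". The lead-in to 8.5.2 describes the content of the section in these words: "The specific risks and our approach to minimize these risks are outlined below".

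**The concern.** The joining word differs. With *and/or*, persistent fasting hyperglycaemia is enough by itself to end the drug-free period. With *and*, it is not, and the only mandatory action in item d for high readings alone is to tell the PI. No text says which version governs.

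The rule protects participants aged 10 to 25 who stop metformin for the run-in, if they were taking it, and again for the washout. Section 8.5.2 is where the protocol sets out how that risk is controlled, and it holds the weaker wording. Someone working from item d alone would not learn that persistent fasting hyperglycaemia without symptoms already requires withdrawal and restart.

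**Working it through.** No power, alpha or sample-size figure is involved. The check sets the rules side by side for each way a participant might present.

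| Presentation while off metformin | Sections 3.2 and 3.2.1 | Section 8.5.2 items d and e |
|---|---|---|
| Persistently high fasting glucose and signs of decompensation | Withdraw and restart | Withdraw and restart (item d) |
| Persistently high fasting glucose, no signs | Withdraw and restart | Notify the PI (item d); no mandatory withdrawal |
| Signs, glucose not persistently high, acidosis or ketosis confirmed | Withdraw and restart | Treat and withdraw (item e) |
| Signs, glucose not persistently high, acidosis or ketosis not confirmed | Withdraw and restart | Evaluate only (item e); no mandatory withdrawal |

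The second and fourth rows differ. In the fourth row, 3.2 and 3.2.1 act on signs and symptoms and give clinical examples, lethargy among them. Item d lists lethargy as a sign too, but item e does not name it as a reason for evaluation. Lethargy without high glucose therefore has no mandatory action under 8.5.2.

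The notification rule, compared in the same way:

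- Level: both texts use fasting above 200 mg/dL. For other times, 3.2.1 uses any reading above 300 mg/dL, and item d names 300 mg/dL at bedtime.
- Period: 3.2.1 is not limited to one period. Item d's sentence names only the run-in, although item 4 is introduced as covering both drug-free intervals.

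In one respect item d is worded more broadly: it refers to glucose levels, whereas 3.2 and 3.2.1 refer to fasting readings. Because item d also requires signs, this does not close the gap in the second row.

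A search for a reconciling rule found none. Section 9.3.1 item 2(b) gives ketoacidosis, or severe hyperglycaemia needing insulin, as examples of adverse events leading to withdrawal. Item 4 of the same list leaves withdrawal to the investigator's judgement. Neither makes persistent fasting hyperglycaemia alone a mandatory reason.

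Time over which the rule operates, using the visit windows in 3.2: run-in 7 to 10 days and washout 14 to 24 days, so 7 + 14 = 21 to 10 + 24 = 34 days per participant. The washout is also given as 2 to 3 weeks (Table 1) and as 21 days (8.5.2), so the range is approximate. It measures time off metformin, not how often the two rules would lead to different actions.

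**The case against.** The strongest reply is that the protective rule is already in force. The two procedural sections state it in the same words, and staff who follow them breach nothing in 8.5.2, because item d does not forbid withdrawal on glucose alone. Item d belongs to a risk narrative whose sub-heading itself pairs hyperglycaemia with decompensation. Other safeguards surround it: entry requires HbA1c below 8% and excludes fasting glucose of 200 mg/dL or more, staff are in daily contact during the run-in, and the hyperglycaemia precautions are reviewed with families before the washout. All of this stands, and it is why the point is minor.

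Two further replies stand in part. Item d's *and* could be read loosely as naming two separate groups, but that is not its plain meaning. Item e could be taken as the work-up by which the team decides whether symptoms amount to decompensation. Even so, 3.2 and 3.2.1 do not make withdrawal wait for laboratory confirmation, and lethargy remains outside item e. It is also true that none of the three statements defines *persistently*, so judgement enters under any version.

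Some stronger readings are tempting, and the documents do not support them:

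- A reader might infer that the protocol requires hyperglycaemic participants to be kept off medication. It does not: 3.2.1 requires withdrawal and restart, and 8.5.2 merely omits that requirement.
- A reader might infer that the washout is unmonitored. Section 3.2.1 provides daily review whenever metformin is stopped.
- A reader might infer that 9.3.1 item 2(b) sets a third, conflicting threshold. It is one of a list of examples, so it neither conflicts with the other sections nor settles the matter.

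**Conclusion.** The inconsistency is real but minor. Taken alone, 8.5.2 falls short of 3.2 and 3.2.1 for persistent fasting hyperglycaemia without signs, and for signs without confirmed acidosis or ketosis. Its notification sentence is narrower in level and in period. It should be corrected because it concerns a safety rule for youths and young adults taken off treatment, and because one reading would let a participant with persistent fasting hyperglycaemia stay off medication.

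The practical effect should be small. That judgement assumes that staff work from 3.2 and 3.2.1 and that daily review is carried out as planned. The documents do not allow the affected participants to be counted; given the entry limits, they should be few. What families are told in Appendix B could not be assessed, because that appendix is not in the available text. No sample size, power or analysis result depends on this point.

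**What to change.** In 8.5.2 item 4.i.d:

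1. Replace the joint condition with the *and/or* condition used in 3.2 and 3.2.1, so that persistently elevated fasting glucose or signs of decompensation each lead to withdrawal and restart.
2. Use the 3.2.1 contact thresholds: fasting above 200 mg/dL, or above 300 mg/dL at any time.
3. State that the item applies in both the run-in and the washout.

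Adding the same criterion to the examples in 9.3.1 item 2 is optional; it would help readers who go straight to the withdrawal section.

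The cost is amendment wording only. The change adds no withdrawal beyond those that 3.2 and 3.2.1 already require, and it leaves the sample size and analysis as they are.
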